Visit 6 will occur 21 (± 3) days following Visit 5 according to the Schedule of Visits and Procedures.

1. Administer efficacy scales (Investigator CGI-S, caregiver and investigator CGI-I, SNAP-IV, CHQ-PF28, PSI-4-SF)
2. Administer Infrequent Behaviors Checklist
3. Administer safety scales (Simpson-Angus, Barnes Akathisia, AIMS)
4. Record height, weight, and BMI
5. Perform 12-lead ECG
6. Perform physical examination
7. Collect blood samples for hematology/chemistry
8. Collect urine sample for urinalysis
9. Administer C-SSRS
10. Record concomitant medication
11. Review IA diary compliance and provide training as required
12. Collect AEs
13. Collect returned SM; assess treatment compliance
14. Review dosing diary compliance and provide training as required
15. Determine whether subject wishes to participate in open-label extension
16. Dispense SM (either Conversion or Taper based upon subject's decision about participation in open-label extension)

4.2.7 Visit 7

Visit 7 will occur 7 (± 1) days following Visit 6 according to the Schedule of Visits and Procedures. These procedures will also be performed for patients who discontinue early. Patients who discontinue early after Visit 5 will be offered a taper kit.

1. Administer safety scales (Simpson-Angus, Barnes Akathisia, AIMS)
2. Record vital signs (HR, BP, temperature, and RR), height, weight and BMI
3. Collect urine sample for pregnancy test (FOCBP only)
4. Administer C-SSRS
5. Record concomitant medication
6. Collect AEs
7. Collect SM and assess treatment compliance
8. Collect device
9. Complete/discontinue subject
10. Collect blood samples for hematology/chemistry
11. Collect urine sample for urinalysis

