6.9.2 Secondary Efficacy Analyses

The secondary endpoints are:

1. Actual Caregiver CGI-I score at Visit 6
2. Actual Investigator CGI-I score at Visit 6
3. Change from Visit 3 to Visit 6 in Investigator CGI-S score
4. Change from Visit 3 to Visit 6 in CHQ-28 score
5. Change from Visit 3 to Visit 6 in PSI-4-SF scores in:
 - a. Parental Distress
 - b. Parent-Child Dysfunctional Interaction
 - c. Difficult Child
6. Change from Visit 3 to Visit 6 in SNAP-IV ADHD scores in:
 - a. Inattention ratings
 - b. Hyperactivity/Impulsivity ratings
 - c. Combined Scale ratings

Each one of the six secondary endpoints will be analyzed using the analysis of covariance method based on the ITT population with missing data imputed using the Last Observation Carried Forward (LOCF) method. The model includes treatment and baseline as fixed independent covariates and change from baseline to final maintenance visit as a response variable. The least squares mean of each treatment group, the difference in the least squares mean (18mg dose minus placebo and 36 mg dose minus placebo), and the 2-sided 95% CI for the difference will be obtained.

To preserve the overall type I error rate at 0.05 for the secondary endpoints, a sequential testing procedure will be used with the following features. First only dose or doses that are significantly different from placebo for the primary endpoint will be tested for secondary endpoints. The first of the secondary endpoints will be compared to placebo using the Hochberg step up procedure but only using those doses retained as a result of testing the primary endpoint (Hochberg 1988). The second secondary endpoint will be tested in the same manner but only using those doses that were retained from the

primary and the first secondary endpoint and so forth. As the endpoints are gone through in the pre-defined order doses will only be retained if significant for all endpoints tested so far and at the given stage the Hochberg step-up procedure will be applied.

The ordering of the 6 secondary endpoints from first to be tested to sixth is: Investigator Clinical Global Impression – Improvement Scale (CGI-I)(Endpoint 1), Clinical Global Impression – Severity Scale (CGI-S) (Endpoint 2), Child Health Questionnaire (CHQ-28) (Endpoint 3), Parenting Stress Index (PSI-4-SF) (Endpoint 4), Caregiver-completed CGI-I (Endpoint 5) and SNAP-IV Rating Scale (Endpoint 6).

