5.2 Secondary Efficacy Variables

1. Actual CGI-I (Investigator-rated Clinical Global Impression – Improvement Scale) score at Visit 6
2. Change from Visit 3 to Visit 6 in CGI-S (Investigator-rated Clinical Global Impression – Severity) score
3. CHQ-PF28 at Visit 6 (Overall Health Measured by Child Health Questionnaire Parent Form 28-item)
4. PSI-4-SF at Visit 6 (Parenting Stress Index – Short Form)
5. Caregiver-completed CGI-I at Visit 6
6. SNAP-IV ADHD scores at Visit 6 (Swanson, Nolan and Pelham-IV Rating Scale for Inattention, hyperactivity-impulsivity and oppositional defiant disorder measured) in
 - Inattention

- Hyperactivity/Impulsivity
- Oppositional Defiant Disorder
- Combined subscale

CGI-I (Protocol Appendix 10.3), relative to the condition at Visit 3, will be evaluated by the caregiver and by the Investigator at Visits 4 to 6 on a 7-point scale with 1=Very much improved, 2=Much improved, 3=Minimally improved, 4=No change, 5=Minimally worse, 6=Much worse, and 7=Very much worse.

CGI-S (Protocol Appendix 10.3) will be evaluated by the Investigator at Visits 1, 3 - 6 on a 7-point scale with 1=Normal, 2=Borderline ill, 3=Mildly ill, 4=Moderately ill, 5=Markedly ill, 6=Severely ill, and 7=Extremely ill.

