The **SNAP-IV** (Protocol Appendix 10.7) rating scale includes 18 ADHD and 8 oppositional defiant disorder (ODD) symptoms as specified in the DSM-IV-TR and International Statistical Classification of Diseases and Health Related Problems 10th Revision (ICD-10) Classification of Mental and Behavioral Disorders. The symptoms are scored by assigning a severity estimate for each symptom on a 4-point scale. The SNAP-IV rating is performed by the parent or legal representative at each visit. The ratings from the SNAP-IV scale are grouped into the following 4 subscales:

- ADHD-Inattention (items #1-9),
- ADHD-Hyperactivity/Impulsivity (items #10-18)
- ODD (items #19-26)
- ADHD-Combined subscale: (items #1 – 18)

Each subscale score is the average of the available item scores in the subscale. The SNAP-IV rating scale will be administered at Visit 3 and Visit 6.

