6.4 Handling of Dropouts, Missing Data, and Data Discrepancies

For the primary analysis of the primary efficacy endpoint, the frequency of IA behaviors during the treatment (titration + maintenance) period will be calculated over the number of days with non-missing IA diary data in the treatment period. No explicit imputation of missing data will be used, but this approach is implicitly equivalent to using the frequency of IA behaviors during the days with non-missing IA diary data to impute the frequency for days after study discontinuation or days with missing IA diary data. In addition to this implicit imputation, multiple imputations under the assumption of missing at random (MAR) and missing not at random (MNAR) will be used for handling missing data for sensitivity analysis. Details of imputation methods are specified in Section [7.7.2](#).

For analysis of frequency of IA behaviors during the treatment period (titration or maintenance), the following methods will be followed.

- 1) If subjects discontinued the study during the maintenance period, their maintenance period will be counted from Visit 5 (exclusive) through the date of last dose as documented on the End of Study eCRF page (inclusive). If the date of last dose is not collected, it will be imputed by the subjects' last visit for the study.
- 2) If subjects have ≥ 7 daily diaries in the maintenance period, their maintenance IA frequencies will be based on maintenance daily diaries.
- 3) If subjects have <7 daily diaries in the maintenance period, their maintenance IA frequencies will be calculated pooling the titration period diaries with the maintenance period diaries.
- 4) If subjects do not have any maintenance diaries, their maintenance IA frequencies will be entirely derived from the titration period diaries.

Missing data for secondary efficacy endpoints will be handled by using the Mixed Model for Repeated Measures method, which is implemented via SAS® PROC MIXED procedure. MMRM assumes data are “Missing At Random (MAR)”. That is, the probability that an observation is missing may depend on the observed values but not the missing values in the previously scheduled visits.

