2. Actual Investigator CGI-I score at Visits 4, 5, and 6 (Table 14.2.3 and Listing 16.2.2.2)
3. Change from baseline (Visit 3) to Visits 4, 5 and 6 in Investigator CGI-S (Table 14.2.4 and Listing 16.2.2.3)
4. CHQ-PF28 Aggregate Physical and Psychological Scores will be summarized at Visit 6 (Table 14.2.5 and Listing 16.2.2.4a – Listing 16.2.2.4c)
5. PSI-4-SF will be summarized at Visit 6 (Table 14.2.6, Listing 16.2.2.5a, and 16.2.2.5b)
 - a. Parental Distress
 - b. Parent-Child Dysfunctional Interaction

- c. Difficult Child
- 6. SNAP-IV ADHD scores will be summarized at Visit 6 in (Listing 16.2.2.6a and Listing 16.2.2.6b):
 - a. Inattention ratings (Table 14.2.7.1)
 - b. Hyperactivity/Impulsivity ratings (Table 14.2.7.2)
 - c. Oppositional Defiant Disorder (Table 14.2.7.3)
 - d. Combined Scale ratings (Table 14.2.7.4)

Scores of CGI-I and CGI-S will be analyzed using a Mixed-Effects Model for Repeated Measure (MMRM). The model includes treatment, visit, and interaction between treatment and visit as fixed factors, baseline CGI-S as covariate for both CGI-I and CGI-S. The model parameters will be estimated using restricted maximum likelihood method with unstructured variance-covariance matrix and Kenward-Roger approximation to estimate denominator degrees of freedom. In case there is a convergence problem in the MMRM model with the unstructured variance covariance matrix, the first (co)variance structure which does not have convergence problem will be used for the analysis from the following ordered list: 1) Toeplitz 2) Autoregressive of order 1 3) Compound symmetry. The least squares mean of each treatment group, the difference in the least squares mean (█ mg dose minus placebo and █ mg dose minus placebo), and the 2-sided 95% CI for the difference will be obtained.

A sample SAS code is provided as follows.

```
PROC MIXED DATA=XXXX ;  
  CLASS trtp(ref="P") usubjid visit;  
  MODEL Response = base trtp visit trtp*visit / DDFM=kr ;  
  REPEATED visit / SUBJECT=usubjid(trtp) TYPE=UN ;  
  Lsmeans trtp*visit/Pdiff alpha=0.05;"  
RUN ;
```

Note: usubjid is subject ID, trtp ("P" denotes placebo treatment) is treatment variable, visit is the nominal study visit, and Response is respective endpoints.

Scores for CHQ-PF28, PSI-4-SF, and SNAP-IV will be analyzed using analysis of variance (ANOVA) at Visit 6.

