To preserve the overall type I error rate at 0.05 for the secondary endpoints, a sequential testing procedure will be used with the following features. First only dose or doses that are significantly different from placebo for the primary endpoint will be tested for secondary endpoints. If the primary endpoint analysis indicates only one dose is significant, no multiplicity adjustment is required. Otherwise, multiplicity adjustment will be performed as in the following. The first of the secondary endpoints will be compared to placebo using the Hochberg step up procedure but only using those doses retained as a result of testing the primary endpoint. The second secondary endpoint will be tested in the same manner but only using those doses that were retained from the primary and the first secondary endpoint and so forth. As the endpoints are gone through in

the pre-defined order doses will only be retained if significant for all endpoints tested so far and at the given stage the Hochberg step-up procedure will be applied.

If the null hypothesis for the primary analysis is not rejected, then no multiplicity adjustment will be done for the secondary endpoints. Otherwise, a sequential testing procedure to preserve the type I error rate at 0.05 will be conducted as described below.

The ordering of the secondary endpoints follows the order in the list above.

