| 14.2.6.1 | Parenting Stress Index – Short Form (PSI-4-SF) Total Score, Change from Baseline to Visit 6 | ITT Population |
| 14.2.6.2 | Parenting Stress Index – Short Form (PSI-4-SF) Parental Distress Subscale Scores, Change from Baseline to Visit 6 | ITT Population |
| 14.2.6.3 | Parenting Stress Index – Short Form (PSI-4-SF) Parent-Child Dysfunctional Interaction Subscale Scores, Change from Baseline to Visit 6 | ITT Population |
| 14.2.6.4 | Parenting Stress Index – Short Form (PSI-4-SF) Difficult Child Subscale Scores, Change from Baseline to Visit 6 | ITT Population |
| 14.2.7.1 | SNAP-IV ADHD Inattention Subscale Score and Change from Baseline to Visit 6 | ITT Population |
| 14.2.7.2 | SNAP-IV ADHD Hyperactivity/Impulsivity Subscale Score and Change from Baseline to Visit 6 | ITT Population |
| 14.2.7.3 | SNAP-IV ADHD oppositional defiant disorder Score and Change from Baseline to Visit 6 | ITT Population |
| 14.2.7.4 | SNAP-IV ADHD Combined Scale Rating Score and Change from Baseline to Visit 6 | ITT Population |
| 14.2.8.1a | Subgroup Analysis of Investigator Clinical Global Impression – Improvement (CGI-I) Score by Visit (Age) | ITT Population |
| 14.2.8.1b | Subgroup Analysis of Investigator Clinical Global Impression – Improvement (CGI-I) Score by Visit (Gender) | ITT Population |

| | | |
|------------|---|-------------------|
| 14.2.8.1c | Subgroup Analysis of Investigator Clinical Global Impression – Improvement (CGI-I) Score by Visit (Race) | ITT Population |
| 14.2.8.2a | Subgroup Analysis of Caregiver Clinical Global Impression – Improvement (CGI-I) Score by Visit (Age) | ITT Population |
| 14.2.8.2b | Subgroup Analysis of Caregiver Clinical Global Impression – Improvement (CGI-I) Score by Visit (Gender) | ITT Population |
| 14.2.8.2c | Subgroup Analysis of Caregiver Clinical Global Impression – Improvement (CGI-I) Score by Visit (Race) | ITT Population |
| 14.3.1.1 | Overall Incidence of Treatment-Emergent Adverse Events by Study Period | Safety Population |
| 14.3.1.2.1 | Incidence of Treatment-Emergent Adverse Events by Preferred Term – Titration and Maintenance Period | Safety Population |
| 14.3.1.2.2 | Incidence of Treatment-Emergent Adverse Events by Preferred Term – Titration Period | Safety Population |
| 14.3.1.2.3 | Incidence of Treatment-Emergent Adverse Events by Preferred Term – Maintenance Period | Safety Population |

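### SAP 7.7.7 drops the baseline covariate for CHQ-PF28, PSI-4-SF and SNAP-IV, and SAP 6.4 sends their missing data to an MMRM that does not include them

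*SAP*

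**What the plan says.** Protocol 6.9.2 applies ANCOVA in the ITT population to each of the six secondary endpoints, with LOCF for missing values: "The model includes treatment and baseline as fixed independent covariates and change from baseline to final maintenance visit as a response variable".

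The SAP, which supersedes the protocol's methods (SAP section 1), splits the endpoints in 7.7.7. CGI-I and CGI-S go into an MMRM with baseline CGI-S as covariate. The other three get one sentence: "Scores for CHQ-PF28, PSI-4-SF, and SNAP-IV will be analyzed using analysis of variance (ANOVA) at Visit 6". SAP 3.6, the section for changes from the protocol's analyses, does not mention this one.

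On the response, SAP 5.2 lists, for example, "PSI-4-SF at Visit 6 (Parenting Stress Index – Short Form"), and the 7.7.7 list also refers to these scales at Visit 6. The Appendix 2 titles differ. CHQ-PF28 and SNAP-IV titles name both score and change, for example "SNAP-IV ADHD Inattention Subscale Score and Change from Baseline to Visit 6". The PSI-4-SF titles read as change from baseline.

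On missing data, SAP 6.4 makes no exception: "Missing data for secondary efficacy endpoints will be handled by using the Mixed Model for Repeated Measures method". The three scales have one scheduled post-baseline assessment. For SNAP-IV, "The SNAP-IV rating scale will be administered at Visit 3 and Visit 6"; CHQ-PF28 and PSI-4-SF follow the same schedule.

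On test order, SAP 7.7.7 says: "The ordering of the secondary endpoints follows the order in the list above". That list puts the three scales 4th to 6th.

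**The concern.** There are three linked problems.

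- **Model.** A baseline value already collected is left out. The same section adjusts CGI-I and CGI-S for baseline CGI-S, so the SAP accepts baseline adjustment in principle.
- **Response.** Without a covariate, the Visit 6 score and the change from Visit 3 are different analyses with different power. The choice is left open until analysis.
- **Missing data.** The stated method cannot act on these scales, because they are outside the MMRM and have no intermediate post-baseline value. The result is an analysis of subjects with a Visit 6 score, although 7.7.7 calls it ITT. That can bias the comparison if dropout differs by arm or depends on response after randomization. Dropout that depends on baseline alike in all arms does not by itself cause bias.

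In the 7.7.7 order, a loss here affects only this last group of endpoints. In the protocol's order (CHQ-PF28 3rd, PSI-4-SF 4th, SNAP-IV 6th), a failure on CHQ-PF28 or PSI-4-SF would also block Caregiver CGI-I, which is 5th. SAP 5.2 lists the endpoints in that same order.

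**Working it through.** The plan gives no power figure for these scales, so there is none to reproduce. The size is an illustration on stated assumptions.

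**Inputs.** Two-sided alpha 0.05 (SAP 7.7.7). Correlation rho between the Visit 3 and Visit 6 scores: not in the documents, assumed 0.3 to 0.7. Equal variances at the two visits and one test per scale are also assumed.

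**Variance of the treatment contrast**, in units of the Visit 6 variance:

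- ANOVA of the Visit 6 score: 1
- ANOVA of change: 2(1 − rho)
- ANCOVA on the Visit 3 score: 1 − rho²

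Relative to ANCOVA, the ratio R is 1/(1 − rho²) for the Visit 6 score and 2(1 − rho)/(1 − rho²) = 2/(1 + rho) for change.

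**Power.** An effect with 80% power under ANCOVA has a standardized value of 1.960 + 0.842 = 2.802. Under another analysis, power = Phi(2.802/√R − 1.96). At rho 0.5, R = 1.33 for either ANOVA, 2.802/√1.333 = 2.427, and Phi(0.467) = 0.68.

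| rho | R, Visit 6 score | Power | R, change | Power | ANCOVA power |
|---|---|---|---|---|---|
| 0.3 | 1.10 | 76% | 1.54 | 62% | 80% |
| 0.5 | 1.33 | 68% | 1.33 | 68% | 80% |
| 0.6 | 1.56 | 61% | 1.25 | 71% | 80% |
| 0.7 | 1.96 | 52% | 1.18 | 73% | 80% |

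ANCOVA is the most precise in every row. Which of the two ANOVAs is worse depends on rho, so the unsettled response matters.

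**Simulation check** with 122 per arm (the evaluable number in SAP 3.5) and 4,000 runs, given as ANCOVA / Visit 6 ANOVA / change ANOVA: 0.80/0.76/0.61 at rho 0.3, 0.80/0.69/0.67 at 0.5, and 0.79/0.52/0.73 at 0.7. These agree with the formula.

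**Why ANCOVA settles the response.** Change is the Visit 6 score minus the Visit 3 score. With the Visit 3 score in the model, switching between the two lowers or raises its coefficient by 1 and leaves the treatment difference unchanged.

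**Tracing a missing Visit 6 score.** SAP 6.2 uses unscheduled data when the next scheduled visit is missing because of early termination. Early discontinuers attend Visit 7 (Protocol 4.6), and Protocol 4.2.7 says of its procedures: "These procedures will also be performed for patients who discontinue early". That list contains none of the three scales, so the rule will seldom supply a value. SAP 3.5 allows 20% dropout, from 153 randomized to 122 evaluable per arm, or 153 − 122 = 31. This is a planning figure and only an approximate guide to how many could lack a Visit 6 score.

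**The case against.** The SAP is entitled to supersede the protocol, and with complete data randomization keeps an ANOVA valid for type I error. That is right. The departure is a loss of efficiency, not a loss of validity, and it is also undeclared in SAP 3.6.

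The SAP's summary of changes says the other secondary endpoints will use ANCOVA, so ANOVA may be a drafting slip. If so, the power loss arises only if the analysis is run as written. The summary does not override the current 7.7.7 text, and the remedy is the same either way.

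The Appendix 2 point is narrower for CHQ-PF28 and SNAP-IV, whose titles name both score and change and may only describe table contents. They still do not say which is tested.

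The protocol is no better model for missing data. With only Visits 3 and 6 scheduled, LOCF would carry the baseline value forward. ANCOVA alone would not recover missing Visit 6 scores either. Protocol 4.2 follows dosed subjects however many doses they took, so fewer than 20% may be missing.

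The magnitude is hypothetical. SAP 7.7.7 has two CHQ-PF28, three PSI-4-SF and four SNAP-IV scores, and two doses under Hochberg, so one test per scale simplifies the real testing. The comparison of methods for any one test is unaffected.

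**Conclusion.** The concern holds. As written, three of the six secondary endpoints are analysed without the baseline adjustment the protocol specifies, on a response that is not settled, and with a missing-data rule that does not apply to them. Over assumed correlations of 0.3 to 0.7, power for an effect with 80% under ANCOVA falls to between 76% and 52% for the Visit 6 score, or to between 62% and 73% for change. These figures rest on the assumed rho, equal variances and one test per scale. The primary analysis is unaffected, and in the 7.7.7 order no CGI endpoint is affected. This should be corrected, but it does not threaten the trial's main conclusion.

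**What to change.** 1. In SAP 7.7.7, replace the ANOVA sentence with: *Change from Visit 3 to Visit 6 in CHQ-PF28, PSI-4-SF and SNAP-IV scores will be analysed by ANCOVA with treatment as factor and the Visit 3 score of the same scale as covariate; LS mean differences from placebo and 95% CIs will be presented.*
2. State the same response in SAP 5.2, the 7.7.7 list and the Appendix 2 titles.
3. In SAP 6.4, limit the MMRM statement to CGI-I and CGI-S, and name a workable method for missing Visit 6 scores on the other three scales. Multiple imputation from the Visit 3 score and available CGI data is one option.
4. Record in SAP 3.6 any remaining departure from Protocol 6.9.2, including the replacement of LOCF.

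The cost is SAP wording and a small code change, with no new data. It should be settled before database lock and unblinding.

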7.7.2.2 Multiple Imputation Assuming Missing Not at Random

This sensitivity analysis assumes that the diary data are missing not at random (MNAR), that is, the probability that an observation is missing may depend on its underlying unobserved value.

This approach may be considered “worst-case” sensitivity analyses as it assumes that after discontinuation subjects from the dosing arms would adopt the outcome model estimated from the placebo arm. To generate missing values from this “placebo-based” imputation model, PROC MI with the MNAR statement will be used (Table 14.2.1.2.2). A sample SAS code is as follows.

```
PROC MI DATA=adqs NIMPUTE=100 SEED=123456789 MINIMUM=0 OUT=adqs_imp ;
  CLASS trtp ;
  VAR age sex bwk twk1 twk2 twk3 twk4 twk5;
  FCS reg ;
  MNAR MODEL(bwk twk1 twk2 twk3 twk4 twk5 / MODELOBS=(trtp='Placebo')) ;
  RUN ;
```

where multivariate imputation is carried out by the fully conditional specification (fcs) method.

7.7.3 *Analysis of PCH Based on Data from Maintenance Period*

For this sensitivity analysis, the primary analysis will be repeated using data restricted to the maintenance period only (Table 14.2.1.2.3).

7.7.4 *Supplementary Analysis*

A supplementary analysis will be performed based on the Per Protocol population and will be presented in Table 14.2.1.2.4.

7.7.5 *Analysis Based on Adjustment of Covariates*

An exploratory analysis of the primary efficacy endpoint will be performed using a randomization-based approach (Dmitrienko and Koch 2017). Separate models will be produced for the following key prognostic baseline characteristics (age [categorical and continuous] and gender [categorical]) will be used in this analysis. In addition, pooled site and baseline IA adjusted to 7 days will be used as covariates (Table 14.2.1.4).

7.7.6 *Examination of Subgroups*

The primary and key secondary efficacy (Caregiver CGI-I and Investigator CGI-I) variables will be summarized by subgroup to explore the heterogeneity of the treatment effect across subgroups. This analysis will be done for the following subgroups: gender (male, female), age (6-9 and 10-12), and race (White, Black/African American, Other) (Table 14.2.1.5a - Table 14.2.1.5c).

7.7.7 *Secondary Efficacy Analyses*

All secondary analyses are based on the ITT population to compare the █ mg dose with the Placebo. The secondary analysis variables are:

1. Actual Caregiver CGI-I score at Visits 4, 5, and 6 (Table 14.2.2 and Listing 16.2.2.2)

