| 14.1.11 | Exposure to Study Medication and Compliance | ITT Population |
| 14.1.12.1 | Prior Medications by ATC Code and Preferred Term | Safety Population |
| 14.1.12.2 | Concomitant Medications by ATC Code and Preferred Term | Safety Population |
| 14.2.1.1 | Analyses of PCH in the Frequency of IA Behaviors During the Treatment Period - Primary Analysis | ITT Population |
| 14.2.1.2.1 | Analyses of PCH in the Frequency of IA Behaviors During the Treatment Period - Sensitivity Analysis, Multiple Imputation with MAR Assumption | ITT Population |
| 14.2.1.2.2 | Analyses of PCH in the Frequency of IA Behaviors During the Treatment Period - Sensitivity Analysis, Multiple Imputation with MNAR Assumption | ITT Population |
| 14.2.1.2.3 | Analyses of PCH in the Frequency of IA Behaviors During the Maintenance Period - Sensitivity Analysis | ITT Population |
| 14.2.1.2.4 | Analyses of PCH in the Frequency of IA Behaviors During the Treatment Period - Supplementary Analysis | PP Population |
| 14.2.1.3 | Descriptive Statistics for Frequency of IA Behaviors Per 7 Days and Change from Baseline by Study Period | ITT Population |
| 14.2.1.4 | Percent Change from Baseline to Treatment Period in Frequency of IA Behaviors: Adjustment for Covariates using Randomization-Based Approach of Dmitrienko and Koch | ITT Population |
| 14.2.1.5a | Analyses of PCH in the Frequency of IA Behaviors During the Treatment Period by Gender - Primary Analysis | ITT Population |
| 14.2.1.5b | Analyses of PCH in the Frequency of IA Behaviors During the Treatment Period by Age - Primary Analysis | ITT Population |

| | | |
|-----------|--|----------------|
| 14.2.1.5c | Analyses of PCH in the Frequency of IA Behaviors During the Treatment Period by Race - Primary Analysis | ITT Population |
| 14.2.2 | Investigator Clinical Global Impression – Improvement (CGI-I) Score by Visit | ITT Population |
| 14.2.3 | Caregiver Clinical Global Impression – Improvement (CGI-I) Score by Visit | ITT Population |
| 14.2.4 | Investigator Clinical Global Impression – Severity (CGI-S) Score and Change from Baseline by Visit | ITT Population |
| 14.2.5.1 | Child Health Questionnaire Parent Form 28 (CHQ-PF28) - Item Scores and Change from Baseline to Visit 6 | ITT Population |
| 14.2.5.2 | Child Health Questionnaire Parent Form 28 (CHQ-PF28)-Component Scores and Change from Baseline to Visit 6 | ITT Population |

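### SAP 7.7.7 sets a secondary test order that conflicts with protocol 6.9.2 and SAP 5.2, leaves the one-dose rule unclear, and claims more error control than its two-dose rule delivers

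*SAP*

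**What the plan says.** **Order.** SAP 7.7.7 closes with "The ordering of the secondary endpoints follows the order in the list above". Its list begins with "Actual Caregiver CGI-I score at Visits 4, 5, and 6 (Table 14.2.2 and Listing 16.2.2.2" and continues with "Actual Investigator CGI-I score at Visits 4, 5, and 6 (Table 14.2.3 and Listing 16.2.2.2". Protocol 6.9.2 has a sentence devoted to the testing sequence: "The ordering of the 6 secondary endpoints from first to be tested to sixth is: Investigator Clinical Global Impression". That sentence then runs through CGI-S, CHQ, PSI-4-SF, Caregiver CGI-I (fifth) and SNAP-IV (sixth). SAP 5.2 lists the variables in the same sequence. Protocol 6.9.2 also has a numbered list of endpoints that starts with "Actual Caregiver CGI-I score at Visit 6". SAP Appendix 2 assigns the tables the other way round from 7.7.7: "14.2.2 | Investigator Clinical Global Impression" and "14.2.3 | Caregiver Clinical Global Impression".

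**One retained dose.** SAP 7.7.7 says that a sequential procedure will be used. It then says that no adjustment is needed if a single dose succeeds on the primary, and introduces the endpoint-by-endpoint gate after the word *otherwise*. A later paragraph says that, once the primary null is rejected, a sequential procedure described below applies. Only the ordering sentence follows.

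**Two retained doses.** Hochberg is applied to the retained doses at each endpoint, and "doses will only be retained if significant for all endpoints tested so far". SAP 7.7.7 takes this rule over from protocol 6.9.2 and says that it preserves an overall 0.05.

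**Precedence.** SAP section 1 says that the SAP supersedes the protocol's statistical methods. SAP 3.6 declares no change to the planned analyses. Protocol 6.1 requires an amendment when a principal feature changes.

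**The concern.** In a gated sequence the order determines which claims can be made at all, because a miss on an early endpoint closes everything behind it. Two orders stand in the governing documents. After unblinding, a reader could defend either one, and the results would show which is more convenient. The one-dose text matters because the design can drop a dose at the interim analysis, and a dropped dose can no longer be declared significant, so a single surviving dose is a realistic outcome. The two-dose text matters because the SAP makes a general statement about error control that a reader would take to hold whichever endpoints each dose truly affects.

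**Working it through.** **1. The orders side by side**

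| Position | Protocol 6.9.2 ordering sentence; SAP 5.2 | SAP 7.7.7 list (the stated test order); protocol 6.9.2 numbered list |
|---|---|---|
| 1 | Investigator CGI-I | Caregiver CGI-I |
| 2 | CGI-S | Investigator CGI-I |
| 3 | CHQ-PF28 | CGI-S |
| 4 | PSI-4-SF | CHQ-PF28 |
| 5 | Caregiver CGI-I | PSI-4-SF |
| 6 | SNAP-IV | SNAP-IV |

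The SAP conflicts with the protocol's testing sentence and with its own section 5.2. Its list matches the protocol's numbered list of endpoints, so the documents do not show whether the change was intended or copied.

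**2. What the order does to the claims**

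Inputs from the documents: fixed sequence, two-sided 0.05. Assumed: one retained dose, every endpoint at 90% power, equal correlation between endpoints of 0, 0.5 or 0.7. With independent endpoints the chance of a claim is 0.90 raised to the position in the sequence: second place 0.90² = 0.81; fifth place 0.90⁵ = 0.59. Simulation gives the correlated cases.

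| Chance of a formal claim | Protocol order | SAP order |
|---|---|---|
| Investigator CGI-I | 90% | 81%, 83%, 85% |
| Caregiver CGI-I | 59%, 71%, 76% | 90% |

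(Values at correlation 0, 0.5, 0.7.) Each order protects a different claim.

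**3. One retained dose, no true secondary effect**

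- Fixed sequence kept: an error needs a false rejection on the first endpoint, so the rate is 0.05.
- Fixed sequence dropped, six endpoints each at 0.05: 1 − 0.95⁶ = 0.265 if independent. Simulated: 26%, 21% and 16% at correlation 0, 0.5 and 0.7.

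The second reading has no gate, so this inflation and the order effect in step 2 cannot both occur.

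**4. Two retained doses**

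Inputs from the documents: Hochberg at 0.05 on the retained doses, carry-forward as above, 1:1:1 allocation. Equal allocation with a shared placebo gives a correlation of 0.5 between the two dose contrasts. Both doses are taken to have passed the primary.

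The stated 0.05 is reproduced when no secondary effect exists: 4.8% at each correlation.

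Now let dose A work on endpoint 1 only and dose B on nothing. Once A is significant, Hochberg tests B at 0.05 on endpoint 1. B usually drops out, and A, alone and null on endpoint 2, is tested there at the full 0.05. With certain detection and independence the error is 1 − 0.95² = 0.0975.

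| Pattern of true effects | Error at correlation 0, 0.5, 0.7 |
|---|---|
| None | 4.8%, 4.8%, 4.8% |
| A on endpoint 1 only (90% power), B none | 8.5%, 7.8%, 7.2% |
| A on endpoint 1 only (near-certain detection), B none | 9.7%, 9.5%, 9.5% |
| A on all six, B none | 4.5-5.0% over the cases run |
| Both on endpoints 1-3 only (90% power) | 4.0%, 3.2%, 2.7% |

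So 0.05 holds in several patterns but not in all. Because protocol 6.9.2 has the same rule, restoring the protocol's order would not change this.

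**The case against.** - **The SAP governs, and any single order fixed in advance holds 0.05 for one dose.** Both statements are right, and they rule out a claim that the SAP order is wrong in itself. They do not say which order applies when SAP 5.2 and the protocol's testing sentence show another and SAP 3.6 declares no change.
- **The SAP order may look harmful because it can block Investigator CGI-I.** A reader might infer this by looking at that endpoint alone. The documents do not support it: Caregiver CGI-I loses more under the protocol order at equal power, and nothing in the documents gives the power of either.
- **The change log may look like evidence of a concealed change.** It tracks edits between SAP versions, not departures from the protocol, and the earlier list is not available. Only the silence of SAP 3.6 bears on whether a change was declared.
- **With one dose, a reader might infer a 16-26% error rate.** That is the less natural reading. The opening sentence and the later paragraph both call for a sequential procedure whenever the primary null is rejected, which favours 5%. The wording is ambiguous; inflation is not established.
- **The two-dose pattern is narrow.** It needs a dose that passed the primary yet affects no secondary, beside a dose whose effect stops after an early endpoint. Under the SAP order the worked example is an effect on Caregiver CGI-I with none on Investigator CGI-I. This limits the practical weight. But the SAP states preservation of 0.05 without conditions, and that statement is what fails.

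**Conclusion.** The point stands as a defect of specification that should be fixed before unblinding. Two secondary test orders stand, and SAP 3.6 does not choose between them. The one-dose sentence can be read with or without the gate, with the gated reading more likely. The claim to preserve 0.05 is too strong for two retained doses: 4.8% with no secondary effects, 7-10% when one dose works on the first endpoint only and the other on none, and about 5% or less in the other patterns examined.

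The document conflict needs no assumption. The percentages rest on assumed endpoint correlations of 0 to 0.7, assumed powers, and one decision per endpoint. The primary analysis and its error control are not affected.

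**What to change.** Before unblinding:

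1. **Order.** State one order in SAP 7.7.7. Either use the protocol 6.9.2 testing sentence, or declare and justify another order in SAP 3.6 and by protocol amendment. Then make SAP 5.2, the 7.7.7 list and its table numbers, and Appendix 2 agree.
2. **One dose.** Replace the sentence with: *With one retained dose no between-dose Hochberg adjustment is needed; the endpoints are tested in the fixed order, stopping at the first non-significant one.* Delete the later paragraph that starts from a non-rejected primary null and refers to a description below.
3. **Two doses.** Keep the protocol's carry-forward and correct the claim: 0.05 holds when all secondary nulls are true, but is not strongly controlled across doses and endpoints when both doses are retained. An optional alternative is one fixed sequence per dose at 0.025 (Bonferroni bound 0.025 + 0.025 = 0.05), declared as a departure from protocol 6.9.2.
4. **Minor wording.** Name the deciding score for CHQ-PF28, PSI-4-SF and SNAP-IV; PSI-4-SF already has a Total Stress score in SAP 5.2 and a table for it in Appendix 2. State Visit 6 as the deciding visit for CGI-I and CGI-S, since 7.7.7 lists Visits 4 to 6 and SAP 5.2 gives Visit 6. Reconcile the singular dose in the opening sentence of 7.7.7 with the two-dose text that follows.

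**Cost.** SAP wording only if the protocol order and carry-forward are kept; another order also needs an amendment. The alternative in item 3 costs power. With each endpoint at 90% power, correlation 0.5, two doses, and 0.025 passed to the other dose after all six succeed, power per dose falls from 88.9% to 86.5% on the first endpoint and from 66.0% to 61.7% for all six.
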